This study is planned as analysis of routinely collected health data in secondary automated electronic data sources in Denmark, Italy, Norway, Spain, and the UK, selected based on availability of the required routinely collected data, including information on vaccine brand and frequency of data updates.

Study size

It is estimated that the number of live births available for analysis will range between 20,000 to 100,000 depending on a data source.

Data analysis

Counts and percentages will be presented for categorical variables (woman's age at conception in categories). Means, standard deviations, medians and interquartile ranges will be presented for continuous variables (woman's age at conception). The proportion of missing data will be described when appropriate. For pregnancy complications and adverse pregnancy outcomes, pregnancy will be the unit of observation; for neonatal outcomes, a newborn will be the unit of observation. For the outcomes of congenital malformations and stillbirth, the number at risk will be the total number of live or stillborn children.

Prevalence of each outcome will be computed as number of observations with a given outcome divided by the total number of observations at risk. Prevalence of each outcome will be compared for exposed vs. unexposed pregnancies according to predefined exposure categories and using, whenever necessary, plausible exposure risk windows. For example, for assessing the outcome of congenital malformations, maternal gestational diabetes and hypertensive disorders, births or pregnancies will be classified based on their exposure in the first (or second, if relevant) trimester. For all other neonatal outcomes, exposure any time in pregnancy and per trimester may be considered.

For neonatal deaths, 28-day mortality risks will be computed and compared among live-born neonates. For pregnancy-related death, maternal mortality will be evaluated at any time while pregnant or up to 1 year after pregnancy end.

All relevant analyses will be stratified by country, maternal age, sex, calendar time, trimester and seasonality if applicable.

Milestones

Data collection will continue through 31 March 2023 with a final study report planned by December 2023.

5. Amendments and updates

Write "None" or indicate any substantial amendment and update to the study protocol after the start of data collection in a table as indicated below.

Confidential

Post-marketing safety study for COVID-19 mRNA-1273 vaccine

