9.1. Study design

9.1.1 Prevalence study

The pregnancy complications, adverse pregnancy outcomes (except pregnancy-related death), and neonatal outcomes (except neonatal death) will be addressed using the prevalence study

design. In the routinely collected data, pregnancies are identifiable on the date of pregnancy end, either in a birth or in an abortive outcome. All identifiable pregnancies will be included, and their start and end dates will be estimated based on the first day of the last menstrual period (LMP) or gestational age at end, depending on data availability. Outcomes examined in this design include gestational diabetes, hypertensive disorders of pregnancy, fetal growth restriction/small for gestational age, abortive outcomes, stillbirth, preterm birth, major congenital malformations, microcephaly (head circumference), and ectopic pregnancy..

Risk of adverse and pregnancy outcomes will be compared in births exposed and unexposed to Spikevax. The measure of association will be prevalence ratio.

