9.1.2 Cohort study

For the outcomes neonatal death, and pregnancy-related death, and postpartum bleeding, a cohort design will be employed.

Risk of neonatal (28-days postnatally) death will be compared in liveborn neonates exposed and unexposed to Spikevax in utero or during the periconceptional period. The measure of association will be the risk ratio.

Pregnancy-related deaths will be assessed by comparing deaths among pregnant women exposed and unexposed to Spikevax between 30 days before LMP and delivery date. A given pregnancy will be considered exposed from the recorded date of the first Spikevax dose receipt. The measure of association will be mortality rate ratio.

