9.2.1 Inclusion Criteria

The study population will include all pregnancies, identifiable in the databases, ending in a live or still birth, a spontaneous abortion, an induced abortion, or an ectopic pregnancy, as identifiable in the participating databases during the study period. In Denmark and Norway, all

pregnancies ending in a live or still birth, as well as pregnancies leading to a hospital encounter due to termination will be identifiable. All pregnancies will be eligible for inclusion.

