9.2.2 Exclusion Criteria

Excluded will be pregnancies with exposure to known teratogenic medications/infections or chromosomal anomalies (for analysis of malformations) and pregnancies with unavailable information on data on pregnancy start or end. Main analyses will be restricted to women without exposure to COVID-19 vaccines other than Spikevax during pregnancy.

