9.2.3 Study Period

In the prevalence study, there is no follow-up per se, as study population will be assembled based on existing (prevalent) outcomes.

In the cohort study, for the outcome of neonatal death, the maximum follow-up will be 28 days postnatally, censored at emigration or end of data. For the outcome pregnancy-related death, the maximum follow-up will be 1 year after pregnancy end,¹² censored by emigration or end of data availability.

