9.9 Limitations of the research methods

An important limitation of the research method is that currently Spikevax is not indicated for use in pregnancy according to the current label, implying that at least at the initial study stages, the number of exposed pregnancies may be low, potentially affecting precision of the resulting estimates of association. Furthermore, owing to typical data flow in routinely collected data, only completed pregnancies (ending in a birth or an abortive outcome) are identifiable. Ongoing pregnancies cannot be identified. A further limitation is heterogeneity of the different data sources in their ability to identify all pregnancy outcomes of interest. Finally, unmeasured confounding due to non-comparability of vaccinated and non-vaccinated pregnancies (healthy or sick vaccinee), at least at the start of the vaccination of pregnant women, cannot be ruled out. If pregnant women with chronic diseases or those taking medication are more likely to be vaccinated, uncontrolled confounding by morbidity will produce an upward bias in the association between vaccination and some AESI, whenever these chronic diseases are themselves associated with adverse outcomes.

A potential misclassification of exposure timing (eg. if LMP is imprecise) may produce a downward bias, if an association exists.

Because, by definition, pregnancy and neonatal outcomes are prevalent outcomes, one cannot enumerate the cohort of conceptuses initiating the follow-up. Early pregnancies that end in a spontaneous abortion and do not lead to a health care record are not detectable in the available data sources. At the same time, shorter pregnancies may be overestimated in the study population because of being identified by pregnancy end.²¹

Finally, for the outcome major congenital malformations, the standard (EUROCAT)¹⁴ definitions recommend follow-up until age 1 year, which will not be available for all neonates in currently defined study populations. This under ascertainment will lower the sensitivity of the outcome, which, if not related to vaccination status, should not bias associations

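### The window for pregnancy-related death in section 9.1.2 conflicts with other sections on either reading, and the plan counts time before pregnancy end that is nearly event-free by selection

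*Protocol*

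**What the plan says.** Protocol section 9.1.2 assigns pregnancy-related death to the cohort design: "Pregnancy-related deaths will be assessed by comparing deaths among pregnant women exposed and unexposed to Spikevax between 30 days before LMP and delivery date". It adds that a pregnancy counts as exposed from the date of the first Spikevax dose, and that the measure is a mortality rate ratio.

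Section 9.2.3 sets a different end point: "For the outcome pregnancy-related death, the maximum follow-up will be 1 year after pregnancy end", with censoring at emigration or end of data. The Abstract (Data analysis) agrees and includes pregnancy itself: "maternal mortality will be evaluated at any time while pregnant or up to 1 year after pregnancy end".

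Section 9.3.1 defines exposure as at least one dose during pregnancy. Table 4 gives any time during pregnancy as the exposure window for this outcome, and all pregnancies as its analysis population. Neither includes days before LMP.

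On how women enter the study, section 9.1.1 says that "pregnancies are identifiable on the date of pregnancy end, either in a birth or in an abortive outcome". Section 9.2.1 says: "The study population will include all pregnancies, identifiable in the databases, ending in a live or still birth, a spontaneous abortion, an induced abortion", and adds ectopic pregnancy. Section 9.2.2 excludes "pregnancies with unavailable information on data on pregnancy start or end". Section 9.9 concedes: "Ongoing pregnancies cannot be identified".

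Section 9.7.3 plans crude and adjusted measures, with Cox regression for rate ratios. It names no time scale.

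**The concern.** There are two separate problems.

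The first is the wording. The sentence in 9.1.2 does not make clear whether its dates bound the deaths or the doses, and each reading contradicts another section. A common program goes to five databases (section 9.6), so one reading will be coded everywhere. If it is the death window, the year in which most observable deaths fall is lost.

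The second is selection. A woman enters only once her pregnancy has a recorded end, so she has in effect survived to that date. The Abstract nevertheless counts time while pregnant, and 9.1.2 splits that time at the dose date. All time before the dose goes to the unexposed group, which lowers its crude rate for a reason unrelated to the vaccine. Section 9.9 states the identification limit but does not draw this consequence for maternal death.

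**Working it through.** **Stated figures.** The protocol gives no event count, death rate or precision for this outcome (Table 3 covers other outcomes), so there is no figure to reproduce.

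**1. The two readings of 9.1.2**

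| Reading | Conflicts with | Effect |
|---|---|---|
| Death window, LMP−30 to delivery | 9.2.3 and Abstract (to 1 year after pregnancy end) | Closes 365 days too early |
| Exposure window, LMP−30 to delivery | 9.3.1 and Table 4 (dose during pregnancy) | Adds 30 days before LMP |

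Assuming a 280-day pregnancy, the death window is 30 + 280 = 310 days. The Abstract's period is 280 + 365 = 645 days, of which the year after pregnancy end is 365/645 = 57%. A window closing at delivery omits all of that year. On either reading, a delivery date does not exist for the abortive and ectopic pregnancies that Table 4 includes.

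**2. Where a death can be observed.** The 30 days before LMP precede the pregnancy, so they hold no events. From LMP to the day before the recorded end, an included woman must be alive, because sections 9.1.1, 9.2.1 and 9.2.2 admit her only through that end. What remains is death on the end date, death where an end was recorded because of it, and death in the year after.

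**3. Crude person-time ratio under no effect.** The 365 days come from 9.2.3. These inputs are assumptions:
- a 280-day pregnancy
- no deaths before pregnancy end and a constant rate r in the year after
- follow-up from LMP
- 10 unexposed women per exposed woman (one of the Table 3 allocation ratios)
- dose on day d

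Per exposed woman:
- Exposed group: 365r deaths over (280 − d) + 365 = 645 − d days.
- Unexposed group: 3650r deaths over 6450 + d days, the d being her pre-dose time.

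Ratio = [365/(645 − d)] ÷ [3650/(6450 + d)] = (6450 + d) / [10 × (645 − d)]

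| d | Calculation | Ratio |
|---|---|---|
| 100 | 6550/5450 | 1.20 |
| 140 | 6590/5050 | 1.30 |
| 180 | 6630/4650 | 1.43 |

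With k unexposed per exposed and doses spread evenly over pregnancy (mean day 140):
- Time from LMP: (645k + 140)/(505k) = 1.33, 1.30 and 1.29 for k = 5, 10 and 20.
- Time from LMP−30: (675k + 170)/(505k) = 1.40, 1.37 and 1.35.

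**4. Cox regression on time since LMP, same assumptions.** Every death falls after day 280, when exposure status is final. The exposed share of deaths equals the exposed share of the risk set, so the hazard ratio is 1.00.

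Now let 10–30% of pregnancies end at day 56–84, with doses spread evenly over 280 days and 9–17% exposed at term (1:10 and 1:5). The expected partial-likelihood score is solved for the hazard ratio h:

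Σ D(t) × [x(t) − hE(t)/(hE(t) + U(t))] = 0

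D is deaths at time t, x the exposed share of those deaths, and E and U the exposed and unexposed women at risk. The solution is h = 0.93 to 0.98. It falls below 1 because, until day 280, deaths come only from women whose pregnancies ended early, while still-pregnant vaccinated women sit in the risk set unable to have an event.

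**The case against.** **The phrase is probably an exposure window.** It follows directly on the words about being exposed or unexposed, and the neonatal-death sentence in the same section is built the same way with a clear exposure window. Section 9.7.5 also uses LMP−30 as an alternative pregnancy start. A reader might infer that the protocol certainly holds two incompatible follow-up periods and will find almost no deaths. The text does not support that: on the exposure reading, 9.2.3 governs follow-up. The objection moves the conflict without removing it. Section 9.3.1 and Table 4 contain no days before LMP, and LMP−30 in 9.7.5 is a sensitivity analysis.

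**Cox regression is the planned model.** A reader might infer that the study will show a spurious excess of deaths in the vaccinated. That holds only for a crude person-time ratio or an unsuitable time scale. On time since LMP the bias is nil or slightly downward. The objection stands for the adjusted estimate. It is incomplete because 9.7.3 also plans crude measures and fixes no time scale. Leaving the time scale to the statistical analysis plan is normal and is not criticised in itself.

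**Some deaths before delivery may still be recorded.** A stillbirth, abortion or ectopic pregnancy may be recorded at or because of the death, so it would go too far to say that no included woman can die by the end of her pregnancy. This stands. The protocol does not say how often it happens, and near event-free time is an inference from its entry rules.

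**Conclusion.** The concern holds in limited form. The 9.1.2 sentence is ambiguous and contradicts another section whichever way it is read, and its end point does not fit all the pregnancies analysed. That needs no assumptions.

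Time before pregnancy end is nearly event-free by selection, yet it is counted and split at the dose. In a crude person-time ratio this produces about 1.2 to 1.4 under no effect, conditional on the stated assumptions about gestation, allocation and dose timing, none of which the protocol supplies for this outcome. Under Cox regression on time since LMP the distortion is about 1.00, or 0.93 to 0.98 with early-ending pregnancies. An inflated or inestimable adjusted result is therefore not established. Correction is still warranted, because this is a listed primary outcome and the change is simple.

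**What to change.** 1. Reconcile the Abstract, 9.1.2, 9.2.3, 9.3.1 and Table 4. State the exposure window (a dose during pregnancy) and the death window (to 1 year after pregnancy end) in separate sentences, and replace the delivery date with pregnancy end.
2. For the main analysis, start risk time at pregnancy end, fix exposure at that date, follow to 1 year or censoring, and use time since pregnancy end as the Cox time scale. This removes the event-free time from crude and adjusted measures alike.
3. Add to 9.9 that deaths in women with no recorded pregnancy end are not captured.

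The cost is protocol wording; no new data are needed. The downside is a narrower estimand: death at or after pregnancy end, not death at any time while pregnant, and the protocol should say so.

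A supplementary count of deaths during pregnancy, from the prenatal-visit and diagnosis codes described in section 12, is optional. That section says these records are generally incomplete on pregnancy outcomes, obtains the preliminary counts from study mRNA-1273-P904, and allows only one data extraction under this protocol. The main correction does not depend on it.

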9.2. Setting

This study will be multi-database, utilizing routinely collected health data of various types in five European countries: Denmark, Italy, Norway, Spain, and the United Kingdom. Pregnancies ending between 06 January 2021 (date of the earliest approval of the COVID-19 Moderna Vaccine in Europe) and up to 31 December 2022 will be identified and classified according to the exposure to Spikevax overall, and according to the trimester of exposure. The study period may be extended if the size of the study population is insufficient to study specific outcomes of interest. The source population comprises persons contributing to each participating database. The study databases are representatives of their source population (see Appendix 1 for details). Briefly, in Denmark and Norway, the registries have full population coverage with respect to the available routinely collected data. The regional databases in Italy (ARS) and Spain (SIDIAP) are representative of the underlying regional populations (Tuscany and Catalonia, respectively). The CPRD is broadly representative of the UK population.

9.2.1 Inclusion Criteria

The study population will include all pregnancies, identifiable in the databases, ending in a live or still birth, a spontaneous abortion, an induced abortion, or an ectopic pregnancy, as identifiable in the participating databases during the study period. In Denmark and Norway, all

pregnancies ending in a live or still birth, as well as pregnancies leading to a hospital encounter due to termination will be identifiable. All pregnancies will be eligible for inclusion.

9.2.2 Exclusion Criteria

Excluded will be pregnancies with exposure to known teratogenic medications/infections or chromosomal anomalies (for analysis of malformations) and pregnancies with unavailable information on data on pregnancy start or end. Main analyses will be restricted to women without exposure to COVID-19 vaccines other than Spikevax during pregnancy.

9.2.3 Study Period

In the prevalence study, there is no follow-up per se, as study population will be assembled based on existing (prevalent) outcomes.

In the cohort study, for the outcome of neonatal death, the maximum follow-up will be 28 days postnatally, censored at emigration or end of data. For the outcome pregnancy-related death, the maximum follow-up will be 1 year after pregnancy end,¹² censored by emigration or end of data availability.

9.3. Variables

9.3.1 Exposure

The exposure will be defined by a record of receipt of at least one dose of Spikevax during pregnancy.

For the purposes of timing of exposure, trimesters of pregnancy will be defined as follows:

- First trimester: from the first day of the last menstrual period (LMP) to LMP+97 days (both dates inclusive);
- Second trimester: from LMP+98 days to earliest of (LMP+202 days, pregnancy end) (both dates inclusive);
- Third trimester: from LMP+203 days (inclusive) until pregnancy end date (not included)

Pregnancies unexposed to Spikevax vaccine will be categorized as unexposed or as exposed to other COVID-19 vaccines and other non-COVID-19 vaccines (influenza, meningococcal disease, pneumococcal disease, rubella, shingles, tuberculosis), overall and trimester-wise. Pregnancies among women who received Spikevax before LMP will be enumerated and may be used as an additional comparator, group size permitting.

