Spikevax was authorised across the European Union (EU), following conditional marketing authorisation by the European Commission on 6 January 2021⁴ and was approved on 08 January 2021 by the United Kingdom (UK) Medicines and Healthcare products Regulatory Agency (MHRA).⁵ Currently, Spikevax is indicated for active immunisation to prevent COVID-19 caused by SARS-CoV-2 in individuals 18 years of age and older.¹ According to the 28 May update the UK Joint Committee on Vaccination and Immunisation recommends that is that COVID-19 vaccines should be offered to pregnant women at the same time as the rest of the population, in line with the age group roll out.⁶ At the same time, a multinational cohort study showed that COVID-19 infection in pregnancy was associated with increased in severe maternal morbidity and mortality and with neonatal complications.⁷ Thus, an uptake of COVID-19 vaccination among pregnant women should be expected. Indeed, as of 21 July 2021 the Danish Health Authority recommended vaccination of pregnant women in second or third trimester, citing similar recommendations in 20 countries. Vaccination of some or all pregnant women is recommended in Denmark⁸ and Spain, permitted in the UK, and permitted with qualifications in Italy, according to Covid-19 Maternal Immunization Tracker, provided by Johns Hopkins University.⁹

Use of COVID-19 Moderna Vaccine in pregnancy and its effect on the mother and the neonate are currently not fully understood.¹⁰ This postauthorisation safety study (PASS), aims to describe use of Spikevax use in pregnancy and to examine any potential association between Spikevax vaccination and pregnancy complications, and adverse pregnancy and neonatal outcomes. This study is a Category 3 Required Pharmacovigilance Activity in the RMP. Safety of the Spikevax in the general population is examined in a separate, dedicated PASS (reference number mRNA-1273-P904)

8. Research question and objectives

The overarching research question is: is there a greater risk or prevalence of pregnancy complications, adverse pregnancy outcomes, or adverse neonatal outcomes following pregnancies exposed to Spikevax compared with pregnancies unexposed to Spikevax?

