9.7.2 Measures of occurrence and measures of association

Prevalence of each outcome will be computed as number of observations with a given outcome divided by the total number of study population members. For neonatal death, a 28-day mortality risk will be the measure of occurrence among live-born infants. Prevalence/risks will be compared according to predefined exposure categories and using, whenever necessary,

plausible exposure risk windows. For example, for assessing the outcome of congenital malformations, births will be classified based on their exposure in the first trimester. For all other neonatal outcomes, exposure any time in pregnancy and per trimester may be considered.

Table 4 summarizes outcome-specific analysis populations and exposure windows.

Table 4 Summary of outcome-specific analysis populations and relevant exposure windows

Outcome	Analysis population	Relevant exposure window
Hypertensive disorders of pregnancy (preeclampsia, eclampsia, gestational hypertension)	All pregnancies	1st or 2nd trimester
Gestational diabetes	All pregnancies	1st or 2nd trimester
Bleeding during pregnancy	All pregnancies	1st or 2nd trimester
Postpartum haemorrhage	All pregnancies	Any time during pregnancy
Pregnancy-related death	All pregnancies	Any time during pregnancy
Fetal death (spontaneous abortion or stillbirth)	A combined population of stillbirths, livebirths, and pregnancies ending in a spontaneous abortion	Any time during pregnancy
Termination of pregnancy for fetal anomaly (TOPFA)	All pregnancies	Any time during pregnancy
Any elective pregnancy termination	All pregnancies	Any time during pregnancy
Ectopic pregnancy	All pregnancies	Any time during pregnancy
Fetal growth restriction/small for gestational age (SGA)	Live births	Any time during gestation
Preterm birth (<37 full gestational weeks)	Live births	Any time during gestation
Low birth weight (<2500 g)	Live births	Any time during gestation
Major congenital malformations	Live or stillbirths/TOPFA (whenever available) without evidence of teratogenic exposure or infection or chromosomal anomaly	First trimester
Microcephaly (based on head circumference)	Live births without evidence of teratogenic exposure or infection or chromosomal anomaly	Any time during gestation
Low 5-minute Apgar score	Live births	Any time during gestation
Neonatal death (death within 28 days of birth)	Live births	Any time during gestation

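### The three trimester windows in 9.3.1 end by different rules: the first has no cut at pregnancy end, and the end date counts for endings up to day 202 but not later

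*Protocol*

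**What the plan says.** Section 9.3.1 opens with the governing definition: "The exposure will be defined by a record of receipt of at least one dose of Spikevax during pregnancy". It then introduces the windows: "For the purposes of timing of exposure, trimesters of pregnancy will be defined as follows". The three windows are:

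- "First trimester: from the first day of the last menstrual period (LMP) to LMP+97 days (both dates inclusive": a fixed 98 days, pregnancy end not mentioned.
- "Second trimester: from LMP+98 days to earliest of (LMP+202 days, pregnancy end) (both dates inclusive": up to 105 days, cut at pregnancy end, end date included.
- "Third trimester: from LMP+203 days (inclusive) until pregnancy end date (not included": cut at pregnancy end, end date excluded.

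Section 9.2.1 admits pregnancies "ending in a live or still birth, a spontaneous abortion, an induced abortion, or an ectopic pregnancy", so many can end before LMP+97. Table 4 (section 9.7.2) uses these windows in two ways. Hypertensive disorders, gestational diabetes and bleeding are analysed among all pregnancies with a first- or second-trimester window. Malformations are analysed with a first-trimester window in a population that includes terminations for fetal anomaly (TOPFA) where available. Sections 9.3.4 and 9.7.4 add trimester subgroups and strata, and section 9.3.2.2 asks for utilization by trimester.

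**The concern.** A dose given after a pregnancy has ended cannot affect its outcome, and a dose on the day it ends is at best ambiguous. The authors wrote an explicit pregnancy-end cut for the second and third windows but none for the first, which is the one most exposed to early endings. Section 9.6 has one common program distributed to all data access providers, so a literal coding of the windows would be repeated in all five databases.

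The end-date rule is a separate inconsistency. A dose on the day of a loss at 20 weeks (day 140) falls inside the second window, while a dose on the day of a term birth falls in no window. Only pregnancies with short gestation can gain exposure this way, so the misclassification would be related to how the pregnancy ended.

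**Working it through.** **No stated figure depends on this.** Table 3 does not use the windows. As a check, its spontaneous-abortion row (16,667 exposed, ratio 5, prevalence 0.2) follows from exp[(1.96 + z) × √((1−p)/(p·n₁) + (1−p)/(p·r·n₁))], which gives 1.049 and 1.057 for 80% and 90% probability. The protocol prints 1.05 and 1.06. These values stay as they are whatever is done to 9.3.1.

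**Step 1: apply the windows exactly as written.** Inputs are the three windows in 9.3.1. Count days from LMP as day 0 and let the pregnancy end on day e. For e ≤ 97 the first window holds 97 − e days after the end, out of 98.

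| End day e | First-window days after the end | Share of 98 days | Window containing a dose on day e |
|---|---|---|---|
| 42 | 55 | 56% | first |
| 56 | 41 | 42% | first |
| 70 | 27 | 28% | first |
| 84 | 13 | 13% | first |
| 97 | 0 | 0% | first |
| 98 to 202 | 0 | 0% | second |
| 203 or later | 0 | 0% | none |

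**Step 2: apply one rule, with the end date excluded throughout.** For e = 56, 70 and 84 the first window shrinks from 98 days to 56, 70 and 84. No day after the end is classified, and the end date is unclassified in every trimester.

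**Step 3: illustrate the size, conditional on literal coding.** The documents give no vaccination rate by gestational day. Assume a constant daily chance of a first dose, the same before and after the loss, with a cumulative 5%, 10% or 17% over 98 days, and no vaccine effect. With daily chance h, the probability of being classed as first-trimester exposed is 1 − (1−h)^98 uncut and 1 − (1−h)^e when cut.

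| Loss on day | Cut → uncut, 5% | Cut → uncut, 10% | Cut → uncut, 17% | Ratio |
|---|---|---|---|---|
| 56 | 2.9% → 5.0% | 5.8% → 10.0% | 10.1% → 17.0% | 1.68 to 1.73 |
| 70 | 3.6% → 5.0% | 7.3% → 10.0% | 12.5% → 17.0% | 1.36 to 1.39 |
| 84 | 4.3% → 5.0% | 8.6% → 10.0% | 14.8% → 17.0% | 1.15 to 1.16 |

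The ratio hardly depends on uptake. At very low uptake it tends to 98/e, that is 1.75, 1.40 and 1.17.

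A weekly version gives the same picture. For a loss on day 63, with weekly chance 1%, 2% or 3%, 1 − (1−h)^9 against 1 − (1−h)^(97/7) gives 8.7% → 13.0%, 16.6% → 24.4% and 24.0% → 34.4%, or 44% to 50% more losses classed as exposed. These absolute shares are high for this study: 1% per week is 1 − 0.99^40 = 33% over 40 weeks, whereas Table 3 plans for 4,762 to 16,667 exposed per 100,000 births (4.8% to 16.7%). Only the ratios carry over.

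**Step 4: direction.** The sign depends on whether the early-ending pregnancies are cases.

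- Bleeding: early losses plausibly carry bleeding codes, so falsely exposed losses would push the ratio up.
- Malformations: a TOPFA is a case, so a TOPFA before LMP+98 falsely classed as exposed would also push it up. Spontaneous abortions are not in this population.
- Losses within a first-trimester stratum: upward.
- Gestational diabetes and hypertensive disorders: a pregnancy lost before LMP+98 seldom becomes a case. Adding such pregnancies to the exposed group enlarges its denominator and pulls the ratio down.

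**The case against.** The strongest reply is that the opening sentence of 9.3.1 governs. Exposure is a dose during pregnancy, and the windows only divide that exposure by timing. A dose on day 80 after a loss on day 60 fails the parent condition whatever the first window says. The protocol also leaves outcome-specific exposure windows to the SAP (section 9.3.2.1).

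This stands against the stronger reading that a reader might infer, namely that post-loss doses count as exposure under the plan and inflate exposed losses by 44% to 50%. The documents do not support it. Table 4 gives fetal death this population and window: "A combined population of stillbirths, livebirths, and pregnancies ending in a spontaneous abortion Any time during pregnancy". TOPFA, elective termination and ectopic pregnancy as outcomes likewise use the whole pregnancy, not a trimester window. The percentage could therefore reach losses only through trimester strata, and only if the parent condition were dropped in coding.

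Nor does section 7 show that vaccination soon after a loss was likely. It reports that "the Danish Health Authority recommended vaccination of pregnant women in second or third trimester", but it also reports UK advice to offer vaccine to pregnant women alongside the rest of the population, and it has no data on vaccination after a loss. A uniform upward bias is not supported either, as step 4 shows.

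The reply does not dispose of two things. The authors did not rely on the opening sentence for the second and third windows, so its silent use for the first is open to misreading. And the sentence does not say whether the end date belongs to pregnancy, which the windows answer in opposite ways. That second gap is real but concerns a single calendar day per pregnancy.

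**Conclusion.** The point holds as an internal inconsistency of minor weight. The first-trimester window, taken literally, conflicts with the parent definition for every pregnancy ending before LMP+97. The end date is exposure for endings up to day 202 and not for later ones, and nothing in the section resolves this.

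If the program keeps the parent condition, only the end-date question remains, affecting a few same-day doses. If the windows are coded alone, first-trimester exposure among early losses would be overstated by about 1.7, 1.4 and 1.15 times for ends on days 56, 70 and 84. This assumes constant uptake before and after the loss and no vaccine effect. The effect on the ratios themselves is not quantified, because the documents do not give the number of early endings or their vaccination pattern, and its sign differs by outcome.

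**What to change.** In 9.3.1, use one end rule for all three trimesters:

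- First: LMP to the earlier of LMP+97 and the day before pregnancy end.
- Second: LMP+98 to the earlier of LMP+202 and the day before pregnancy end.
- Third: LMP+203 to the day before pregnancy end.

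Add that a dose on or after the pregnancy end date is not exposure for that pregnancy, and apply the same rule to the whole-pregnancy window. Including the end date everywhere would also be consistent, but excluding it keeps the existing third-trimester rule and avoids counting doses given after the event on the same day.

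The cost is three lines of text and one condition in the common program. It is feasible because section 9.2.2 already excludes pregnancies without a known start or end. The only loss is that a few same-day doses leave the exposed group.
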